12.9. Publication Policy

- The results of this study may be published or presented at scientific meetings. If this is foreseen, the investigator agrees to submit all manuscripts or abstracts to the sponsor before submission. This allows the sponsor to protect proprietary information and to provide comments.
- The sponsor will comply with the requirements for publication of study results. In accordance with standard editorial and ethical practice, the sponsor will generally support publication of multisite studies only in their entirety and not as individual site data. In this case, a coordinating investigator will be designated by mutual agreement.
- Authorship will be determined by mutual agreement and in line with International Committee of Medical Journal Editors authorship requirements.

13. Statistical Considerations

Based on previous feasibility data, a sample size of 600 patients per arm (1:1 allocation, 1,200 total in both arms) would provide >99% Power to detect superiority for APC assuming a data loss of 15%. This same number of patients would also provide 90% Power to detect superiority for ADR, based on the expected ADR of 35% in the control arm, and 45% for the intervention arm. Based on the assumption that PPA will be at least 70% in both arms, Power for the PPA non-inferiority comparison will be > 90%.

The co-primary endpoint of PPA will be tested for non-inferiority using a non-inferiority margin of 10%. PPA will be calculated for each arm as the number of positive biopsies of total removed lesions. A resampling distribution of the difference in PPA will be used to calculate a two-sided 95% confidence interval for the difference: PPA(intervention)-PPA(control). Non-inferiority will be concluded if the lower confidence limit of the 95% two-sided confidence interval is above -10%. For APC, superiority will be assessed based on a one-sided test of the difference in mean rates at a 0.025 level of significance. For ADR, superiority will be assessed using a stratified CMH test at a one-sided 0.025 level of significance.

Interim analysis: When approximately 600 subjects have completed the trial, an interim analysis will be conducted, and a conditional power analysis will be performed. The conditional power will assess the probability (power) that the study will meet its objectives on the superiority endpoint of APC and ADR, and on the non-inferiority of the PPA endpoint. If the conditional power is below 90% for either one of the co-primary endpoints or for ADR, an increase in the sample size from 1200 up to 2400 will be considered.

CPR, Protocol, Gastroenterology Artificial INtelligence System for detecting colorectal polyps (The GAIN Study) Document Number:

The increase in the sample size will be based on the probability of achieving success on both co-primary endpoints (APC and PPA) and success on the ADR endpoint. If the increase in sample size leads to an increase in the power for these endpoints to approximately 90%, then the study will enroll the additional subjects to allow the increase in power. Otherwise, the study may continue to the originally planned sample size of 1200 or stopped for futility. Due to a possible increase in the sample size, the final analysis will be done using a simple combination test, by transforming the test statistics of the interim patients, and the test statistic of the post-interim patients to standard normal (Z) statistics. Using prespecified weights of w1 = 1/2 and w2 = 1/2, the final Z = $\sqrt{w1}$ * interim Z + $\sqrt{w2}$ * post-interim Z. The interim analysis will be conducted by an independent statistician. Recommendations will be communicated confidentially to a select committee within Verily not directly involved in the study. Communication processes will be laid out in the interim analysis section of the statistical analysis plan.

The co-primary endpoints of APC and PPA will be analyzed using the ITT population. Sensitivity analyses will be conducted to assess the effect of missing complete or partial data by considering various imputation methods and will be described in the Statistical Analysis Plan. Subgroup analysis will include assessments of APC, ADR and PPA in groups defined by age-group, sex, race, ethnicity, site, colonoscopist and country

Of the subjects receiving intervention, a subset of subjects may receive an iteration of the device that incorporates varying hardware and software configurations (see Section 11.1). The predicted result of these variations is not expected to significantly impact primary or secondary endpoints.

The Intent to Treat (ITT), modified Intent to Treat (mITT) and Per Protocol (PP) populations will be further defined within the Statistical Analysis Plan.

15. References

CPR, Protocol, Gastroenterology Artificial INtelligence System for detecting colorectal polyps (The GAIN Study) Document Number:

- 8. US Preventive Services Task Force, Davidson KW, Barry MJ, et al. Screening for colorectal cancer: us preventive services task force recommendation statement. JAMA. 2021;325(19):1965-1977. doi:10.1001/jama.2021.6238

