Study Endpoints	 Co-Primary Endpoints Difference in Adenomas Per Colonoscopy (APC) between the control and intervention arm, evaluated for superiority on the Intent To Treat (ITT) population Difference in Positive Percent Agreement (PPA) between the control and intervention arm, evaluated for non-inferiority on the Intent To Treat (ITT) population Secondary Endpoints Adenoma Detection Rate (ADR) evaluated on the ITT population APC, ADR and PPA endpoints evaluated on the Per-Protocol (PP) population APC, ADR and PPA endpoints evaluated on a modified Intent-to-Treat (mITT) population APC, ADR and PPA in subgroups defined by age group, sex, risk-group, race, ethnicity, colonoscopist, site, and country False Alert Rate (FAR) Mean Withdrawal (inspection) Time (MWT) Polyp Detection Rate (PDR) Frat Adenoma Detection Rate (fADR) Serrated Lesions per Colonoscopy (SLPC) Serrated Lesions Detection Rate (sADR) Adenoma Detection Rate including Carcinoma (ADR*) Small Adenoma Detection Rate (sADR) Polyps per colonoscopy (PPC) Advanced Adenoma Detection Rate (aADR) False Positive Rate (FPR) 			

VerilyCPR, Protocol, Gastroenterology Artificial INtelligence System for detecting colorectal polyps (The GAIN Study)
Document Number:

Study Phase	Not applicable		
Study Type	This is a prospective multicenter, randomized controlled study.		
Regulatory Status/Trial Classification	Non-significant risk		
Study Population	A minimum of 1,200 subjects will be enrolled at a minimum of 3 sites, with a possibility of a sample size increase up to 2,400. At least 51% of the study population will be enrolled within the United States.		
User population	Colonoscopists having performed at least 1,000 colonoscopies with a self-reported Adenoma Detection Rate between 25% and 40%. No single colonoscopist will enroll more than 15% of the total patient population.		

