5.3. Primary Endpoint(s)

- Both co-primary endpoints are evaluated on the Intent to Treat (ITT) population.
- Adenomas Per Colonoscopy Co-Primary Endpoint

Difference in Adenomas Per Colonoscopy (APC) between the control and intervention arm, evaluated for superiority.

The APC co-primary endpoint is a test of superiority. The null and alternative hypotheses for establishing superiority are as follows, where APC(I) and APC(C) are Intervention and Control arms APCs respectively:

Ho: $APC(I) \leq APC(C)$

Ha: APC(I) > APC(C)

A statistical test of this hypothesis will be conducted.

• Positive Percent Agreement (PPA) Co-Primary Endpoint

Difference in Positive Percent Agreement (PPA) between the control and intervention arm, evaluated for non-inferiority.

The PPA co-primary endpoint is a non-inferiority comparison based on the difference in PPA across arms. For non-inferiority, the goal of the study is to show that the effect of Intervention (I) is not inferior to the effect of Control (C) by a pre-specified amount, i.e., the NI margin (M). The null and alternative hypotheses are as follows:

Ho: $PPA(I) - PPA(C) \le M$ (I is inferior to C)

Ha: PPA(I) - PPA(C) > M (I is not inferior to C)

A statistical test of Ho will compare the lower bound of the two sided 95% confidence interval for PPA(I)-PPA(C) with M, which is pre-specified as -10%. If the lower bound lies above M, non-inferiority of I relative to C will be established.

• As co-primary endpoints, there are no issues related to multiple testing as both tests must successfully reject H0 in order to declare overall endpoint success.

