7.2.3. Randomization/Blinding/Masking

Enrolled subjects will be randomized into control or intervention arms in a 1:1 allocation using block randomization within subjects strata defined by age-group, sex, and risk-group. Subjects will be assigned to control or intervention arms within each colonoscopist based on a predetermined randomization schedule.

Subjects, investigators, study site personnel, and pathologists will not be blinded to treatment assignments. All Verily personnel involved in the statistical analysis of this study will be blinded to treatment assignment. For the interim analysis, unblinded analysis will be performed by an independent statistician, the results of which will be communicated to a select group of Verily personnel not involved in the study management.

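### The co-primary APC test names no randomisation factors or variance estimator; adjusting for the factors already used to randomise is a small, nearly free gain, not a validity correction

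*Combined protocol and SAP*

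**What the plan says.** **Randomisation (protocol Section 7.2.3).** Allocation is 1:1 using "block randomization within subjects strata defined by age-group, sex, and risk-group". The next sentence adds a fourth factor: "Subjects will be assigned to control or intervention arms within each colonoscopist based on a predetermined randomization schedule". The Protocol Summary limits concentration: "No single colonoscopist will enroll more than 15% of the total patient population". At least seven colonoscopists are therefore needed (100/15 = 6.7).

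**APC analysis.** Section 5.3 gives the superiority hypotheses and then says "A statistical test of this hypothesis will be conducted". Section 13 gives the direction, the scale and the level: "For APC, superiority will be assessed based on a one-sided test of the difference in mean rates at a 0.025 level of significance". Neither section names a stratum, a covariate or a variance estimator for APC. Three of the four factors (age group, sex and colonoscopist) return in Section 13 as APC subgroups, and Section 5.4 lists all four as subgroups.

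**ADR analysis.** The following sentence of Section 13 reads "For ADR, superiority will be assessed using a stratified CMH test". It does not list the strata.

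**Interim.** The final analysis combines two stages "by transforming the test statistics of the interim patients, and the test statistic of the post-interim patients to standard normal (Z) statistics", with weights of 1/2 each.

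**Deferral.** The protocol leaves the analysis populations, imputation methods and interim communication to a separate SAP, which is not in the text reviewed. It does not expressly leave the APC model to that document.

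**The concern.** Blocking on prognostic factors balances them across arms, so the difference in means varies less from trial to trial than it would under simple randomisation. An ordinary two-sample standard error does not register this. It still includes the between-stratum variation, so it overstates the uncertainty and the test rejects slightly less often than its nominal level.

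Two things are at stake. The first is a little power on a co-primary endpoint, from information the trial already collects. The second is an open analyst choice. A difference in mean rates for a count endpoint can be tested with several variance estimators, with or without covariates, and that choice feeds the APC statistic used at an unblinded interim where the sample size may be raised to 2,400.

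**Working it through.** **1. The plan's own figures.**
- Evaluable patients: 1,200 × 0.85 = 1,020, or 510 per arm.
- ADR, 35% against 45%, one-sided 0.025. The null SE is √(2 × 0.40 × 0.60/510) = 0.03068 and the alternative SE is √((0.35 × 0.65 + 0.45 × 0.55)/510) = 0.03052. Power = Φ((0.10 − 1.96 × 0.03068)/0.03052) = 90.4%, which agrees with the stated 90%.
- APC power above 99% cannot be reproduced, because no APC mean, difference or SD is given. For scale, 99% power needs a difference of (1.96 + 2.326) × SD × √(2/510) = 0.268 × SD. That is 0.27, 0.32 or 0.40 for assumed SDs of 1.0, 1.2 or 1.5.

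**2. Analytic size of the effect.** Let R² be the share of APC variance explained by the randomisation factors. The documents do not give it, and 2–5% is assumed here. The unadjusted SE is too wide by k = 1/√(1 − R²). If the adjusted test has power P, its drift is d = z_P + 1.96, which is 4.286 at 99% and 3.242 at 90%. The unadjusted test then has power Φ(d − 1.96k) and true one-sided level 1 − Φ(1.96k). Both stage statistics shrink by the same k, so this holds for the combined Z whatever the stage split.

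| Assumed R² | k | True level | Power if adjusted is 99% | Power if adjusted is 90% |
|---|---|---|---|---|
| 0.02 | 1.010 | 0.0239 | 98.95% | 89.65% |
| 0.05 | 1.026 | 0.0222 | 98.86% | 89.08% |

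The loss is 0.05–0.14 points at 99% and 0.35–0.92 points at 90%. In patients, 1,020 × [1 − ((d − 1.96k + 1.96)/d)²] gives 9.4 and 12.5 at R² = 0.02 (99% and 90% power), and 24.1 and 31.8 at R² = 0.05.

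**3. Simulation with the two-stage combination (all effects assumed).** There were 1,020 patients in permuted blocks of 4 within colonoscopist × age × sex × risk cells, with 7 or 12 colonoscopists and Poisson or negative binomial counts. Two stages of 510 were combined with weights of 1/2 each, without a sample size increase. The adjusted analysis was a linear main-effects model with HC2 variance.
- Mean SE ratio, unadjusted to adjusted: 1.021–1.031, implying R² of 0.041–0.060.
- SD of the estimate, unadjusted/adjusted: 0.0403/0.0403, 0.0809/0.0808, 0.0415/0.0413 and 0.0846/0.0844. The estimate is about equally precise either way; what changes is the reported SE.
- Null rejection (20,000 runs per setting): 0.0222–0.0235 unadjusted and 0.0249–0.0258 adjusted, Monte Carlo SE 0.0011.
- Power near 93% (8,000 runs per setting): gains of 0.4–1.0 points, for example 0.9291 to 0.9386. Above 99%: 0.9965 to 0.9980 and 0.9989 to 0.9991.

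**4. Separate one-stage simulation (14 colonoscopists, 4,000 runs per scenario).** With moderate factor effects, null rejection was 0.0243 unadjusted and 0.0258 adjusted, and power went from 92.6% to 93.5%. With strong effects the null figures were 0.0210 and 0.0248, and power went from 89.5% to 91.7%. In the strong case under the null, the unadjusted SE averaged 0.0709 against a true spread of 0.0688, and the adjusted SE averaged 0.0682 against 0.0685. That case implies R² = 1 − (0.0682/0.0709)² = 0.075, above the 2–5% range in step 2.

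**The case against.** The strongest reply is that no error has been shown. Section 13 fixes the scale, direction and level of the APC test. Its wording is compatible with adjustment, and covariates and variance estimators are usual SAP content. All of that stands. A reader might infer that APC will be analysed unadjusted, but no section says so, and the separate SAP may already settle it.

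A reader might also infer from the word stratified that ADR is fully specified and only APC is not. The ADR sentence names no strata, so the contrast is one word, and the same repair is owed to both tests.

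The size can be overstated too. Larger losses appear if R² is set at 10% or true APC power at 80%, but neither figure is in the documents, and the only APC planning figure is above 99%. The 510 per stage in the simulation is likewise an assumption: the interim falls at about 600 completers, and the text does not say where the 15% loss occurs.

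Finally, the combination test does not need the same APC statistic in both stages to be valid. It needs a valid, prespecified statistic in each. One shared definition is sensible practice, and nothing in Section 13 suggests that two are planned.

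What survives is narrow. The randomisation factors are fixed and recorded, the APC sentence does not use them, and using them is nearly free.

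**Conclusion.** The point holds as an optional improvement. If APC is tested with an ordinary two-sample comparison, the result is valid and slightly conservative. At an assumed R² of 2–5% the SE is 1.0–2.6% too wide. The cost is under 0.15 power points at 99% power and up to about 1 point if true power is nearer 90%.

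A reader might take this for a validity fault or an inflated type I error. The opposite is the case: the true one-sided level lies at or below 0.025.

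The conclusion rests on the assumed R² and on a broadly similar device effect across colonoscopists. The lower-power case is a possibility that cannot be excluded, because the APC inputs are not stated; it is not a planning figure.

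**What to change.** In Section 13 or the SAP:

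- Prespecify APC as the difference in mean adenomas per colonoscopy from a linear model with arm, age group, sex, risk group and colonoscopist as main effects and HC2 variance. This keeps the stated scale and allows for overdispersed counts. Main effects avoid the sparse cells of full crossing (84 to 216 cells in the simulated settings).
- Fix a pooling rule for small colonoscopist groups before any unblinding. For example, colonoscopists with fewer than 20 patients in a stage form one group, and if that group still has fewer than 20 it is merged with the next smallest colonoscopist. The merge step matters: without it some 12-colonoscopist fits gave an infinite HC2 standard error, probably from a pooled group of one patient. The 12-colonoscopist result above 99% power was run without that step; the other 12-colonoscopist figures in the two-stage simulation include it.
- Fit the model separately in interim and post-interim patients and enter each adjusted Z in the combination.
- Keep the unadjusted difference in means with empirical variance as a sensitivity analysis.
- Name the strata of the ADR CMH test in the same edit.
- If the separate SAP already specifies the APC model, cross-reference it in Section 13 instead.

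The cost is a few sentences and a few lines of code. Every factor is already needed for randomisation, so no new data are collected.

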5.4. Secondary Endpoints

• Adenoma Detection Rate (ADR)

The Adenoma Detection Rate is defined as the number of patients with at least one histologically confirmed adenoma (the pathology findings that count as positive for adenoma are defined in Section 5.2) divided by the total number of patients enrolled per study arm.

- Evaluation of ADR on the ITT population
- Evaluation of the APC, ADR and PPA endpoints on the Per-Protocol (PP) population
- Evaluation of the APC, ADR and PPA endpoints on a modified Intent-to-Treat (mITT) population that includes only patients in the Screening and Surveillance risk groups

- Subgroup analysis of APC, ADR and PPA in groups defined by age group, sex, risk-group, • site, race, ethnicity, colonoscopist, site, and country
- False Alert Rate (FAR) •

A false alert is defined as a bounding box that persists on the screen (approximately 2-3 seconds per the judgment of the colonoscopist) that is then determined by the colonoscopist not to contain a polyp. The false alert rate is calculated as the number of false alerts per procedure conducted in the intervention arm of the study.

Mean Withdrawal and Inspection Time (MWT) •

The withdrawal time is defined as the time measured from the moment the withdrawal phase of the procedure begins (with the scope in the cecum) to the moment the scope is withdrawn from the patient. The mean Inspection time measurement (also called net withdrawal time) will exclude resection time, and other peri-resection activity not deemed to be colonic inspection. Inspection times for both the control arm and intervention arm will be calculated retrospectively upon review of the video recordings.

Polyp Detection Rate (PDR) •

> Polyp detection rate is defined as the proportion of patients with at least one histologically-confirmed polyp detected.

Proximal Adenoma Detection Rate (pADR) •

pADR is defined as the proportion of patients with at least one histologically-confirmed adenoma (the pathology findings that count as positive for adenoma are defined in Section 5.2) detected in proximal colon (caecum, ascending colon, hepatic flexure, transverse colon).

Flat Adenoma Detection Rate (fADR)

fADR is defined as the proportion of patients with at least one histologically-confirmed non-polypoid adenoma (the pathology findings that count as positive for adenoma are defined in Section 5.2) detected;

Serrated Lesions per Colonoscopy (SLPC) •

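### ADR is tested for superiority at the full one-sided 0.025 with no condition on the co-primaries, so error is not held at 2.5% across co-primary success and ADR together

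*Combined protocol and SAP*

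**What the plan says.** Section 5.3 names two co-primary endpoints, APC (superiority) and PPA (non-inferiority, margin -10%), and says: "As co-primary endpoints, there are no issues related to multiple testing as both tests must successfully reject H0". ADR appears in Section 5.4 among the secondary endpoints, with the entry "Evaluation of ADR on the ITT population".

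Section 13 gives ADR more than a descriptive role:

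- **Test.** "For ADR, superiority will be assessed using a stratified CMH test at a one-sided 0.025 level of significance". APC has the same level: "For APC, superiority will be assessed based on a one-sided test of the difference in mean rates at a 0.025 level of significance". The PPA rule, a two-sided 95% interval set against -10%, is also one-sided 0.025.
- **Power.** 90% is claimed with 600 patients per arm, "based on the expected ADR of 35% in the control arm, and 45% for the intervention arm".
- **Interim.** Conditional power under 90% for ADR alone is enough to open consideration of an increase from 1,200 towards 2,400. The size of any increase depends on the probability of "success on both co-primary endpoints (APC and PPA) and success on the ADR endpoint".

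No section places ADR after the co-primaries, shares alpha with it, or says what may be stated about ADR if APC or PPA fails.

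**The concern.** The argument in Section 5.3 is correct for the pair it covers: when both tests must reject, neither level needs adjusting. It does not extend to a third hypothesis with its own 0.025. As Section 13 reads, two formal statements can be made independently of each other, co-primary success and ADR superiority. Each has error 2.5%, so the chance that at least one is false can exceed 2.5%.

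A second consequence is separate. PPA is there to show that extra detection does not come with too many excisions that prove not to be clinically significant. Because the ADR test does not depend on PPA, an ADR superiority statement can be made when PPA non-inferiority has not been shown. Section 4.1 describes ADR as the main quality indicator colonoscopists rely on, so such a statement would carry weight.

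**Working it through.** **Inputs from the documents.** ADR 35% against 45%, 600 per arm, 15% data loss (stated in Section 13 with the APC power), APC power above 99%, PPA power above 90%, each test at one-sided 0.025. **Assumed**, because the documents give no values: the correlation between the APC and ADR statistics, and the probability that PPA passes. Each test is taken to hold its nominal level.

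**1. The plan's ADR power.** Evaluable per arm: 600 × 0.85 = 510. With pooled null variance,

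power = Φ{[0.10 × √510 − 1.96 × √(2 × 0.40 × 0.60)] / √(0.35 × 0.65 + 0.45 × 0.55)} = Φ{(2.258 − 1.358) / 0.689} = Φ(1.306) = 90.4%.

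The stated 90% is reproduced. Without the 15% loss (600 per arm) the result is 94.3%, so the loss appears to have been applied to ADR as well.

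**2. APC and ADR both null, PPA truly non-inferior and almost certain to pass.** Co-primary success then has probability of about 0.025, and

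P(at least one false claim) = 0.025 + 0.025 − P(both statistics exceed 1.96).

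| Assumed correlation | P(both) | P(at least one) |
|---|---|---|
| 0.5 | 0.0046 | 4.5% |
| 0.7 | 0.0083 | 4.2% |
| 0.9 | 0.0148 | 3.5% |

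The same adenomas feed both endpoints, so a positive correlation is expected. Count models with 35% of patients positive imply a correlation of about 0.89 (Poisson) down to 0.61 (strongly overdispersed, assumed APC 1.2). Simulation with 510 per arm and assumed APC of 0.45 to 1.0 gave 3.6% to 4.5%.

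If PPA passes only with probability q, independently of the other two tests, the figure is 0.025 + q × (0.025 − P(both)). At q = 0.5 this gives 3.5%, 3.3% and 3.0% for correlations 0.5, 0.7 and 0.9.

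**3. APC truly better, PPA exactly at -10%, ADR null.** Here the false claims are PPA non-inferiority (and with it co-primary success) and ADR superiority. With APC certain to pass and the PPA and ADR statistics independent, the result is 1 − 0.975² = 4.9%. Independence is a bound, because confirmed adenomas enter the PPA numerator and also define ADR. Simulation under assumed lesion counts, with a PPA-ADR correlation of about 0.54 to 0.60, gave 4.4% to 4.7%.

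**4. ADR truly 35% against 45%, PPA at the margin.** An ADR win with PPA failing has probability 0.904 × 0.975 = 88% under independence. It cannot be below 0.904 − 0.025 = 88% whatever the dependence. This is not an error rate, since ADR really is better in this case.

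**5. Effect of a gate.** The probability of a formal ADR claim becomes P(APC and ADR both reject) × PPA power, with PPA taken as independent. With APC power 99%, ADR power 90% and correlation 0.5 to 0.7, the first factor is 0.895 to 0.898.

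| PPA power | Gated ADR claim |
|---|---|
| 90% | 81% |
| 95% | 85% |
| 99% | 89% |

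With independence throughout and PPA power 90%, it is 0.99 × 0.90 × 0.90 = 80%.

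**The case against.** The strongest reply is that ADR is labelled secondary, and that Section 5.3 reserves trial success for the co-primaries: "both tests must successfully reject H0 in order to declare overall endpoint success". On that reading nothing confirmatory hangs on ADR, and the family used above is one the protocol never defines. This stands in part. The protocol does not call ADR confirmatory; that role is inferred from its alpha, its stated power and its part in the interim decision. The reply does not explain why a descriptive endpoint would have a superiority test at 0.025 and be able to prompt a larger trial.

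It can also be said that Section 13 speaks of joint success on APC, PPA and ADR. That wording governs the choice of sample size and is not a testing order. The combination test in the same section deals with the sample-size change, not with several endpoints.

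The protocol also refers some details (populations, imputation, interim communication) to a statistical analysis plan, and no separate plan text is in the document available. Multiplicity is not among the items referred, but a gate there cannot be excluded.

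Stronger readings are tempting and should be resisted:

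- A reader might infer that ADR can rescue a failed trial. Section 5.3 rules that out for overall success; what the text leaves open is a separate ADR statement.
- A reader might treat an ADR win beside a failed PPA as a false positive. ADR counts patients with a confirmed adenoma, and removing non-adenomas does not raise it.
- A reader might add the per-protocol and mITT evaluations of ADR, or the other secondaries, to the error rate. Section 13 gives no test level for any of them.

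**Conclusion.** The gap is real but limited. The co-primary claim is controlled at one-sided 2.5% and is unaffected. For co-primary success and ADR superiority together, the chance of at least one false claim is about 3.5-4.5% when APC and ADR are null and PPA almost surely passes, and lower if PPA often fails. It is at most 4.9% when APC is better, PPA is at -10% and ADR is null, and probably nearer 4.4-4.7%. All of these rest on assumed correlations and on reading ADR as a formal claim. The freedom to state ADR superiority beside a failed co-primary is a separate question of interpretation. Both conclusions are limited to the protocol text. This is a cheap improvement, not a flaw in the primary analysis.

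**What to change.** In Section 13, state that ADR on the ITT population is formally tested at one-sided 0.025 only if both co-primary null hypotheses are rejected, and is otherwise reported as an estimate with a 95% confidence interval and no superiority claim. Add a cross-reference in Section 5.3. With this fixed sequence, the error across co-primary success and ADR is at most 2.5%. No alpha is split, the APC, PPA and ADR test levels stay as they are, and no patients are added.

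The cost is that no formal ADR claim is possible if APC or PPA fails. The chance of such a claim falls from about 90% to about 81-89% as PPA power goes from 90% to 99%. The plan already sizes for success on all three endpoints, so the gate fits its own target. If ADR is meant only as supportive, saying so would also close the point.

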12.5. Interim Analysis Structure

An independent statistician will be utilized for the interim analysis. Within Verily and/or a designee, data and programming for the interim analysis will be performed by an interim analysis dedicated group who are not involved in the management of the study. This group will

communicate with the independent statistician and will provide the unblinding codes. The independent statistician will execute the unblinding with the set of programs prepared by the interim analysis dedicated group and will then communicate the results to a pre-selected group within Verily not involved in the management of the study. A detailed unblinding and a communication plan will be provided in the statistical analysis plan.

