12.8. Study and Site Closure

The sponsor designee reserves the right to close the study site or terminate the study at any time for any reason at the sole discretion of the sponsor. Study sites will be closed upon study completion. A study site is considered closed when all required documents and study supplies have been collected and a study-site closure visit has been performed.

The investigator may initiate study-site closure at any time, provided there is reasonable cause and sufficient notice is given in advance of the intended termination.

Reasons for the early closure of a study site by the sponsor or investigator may include but are not limited to:

- Failure of the investigator to comply with the protocol, the requirements of the IRB/IEC or local health authorities, the sponsor's procedures, or GCP guidelines
- Inadequate recruitment of subjects by the investigator
- Discontinuation of further study intervention development

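### Does the interim rule let a trial that is on course for both co-primary endpoints be stopped as futile because of the secondary endpoint ADR?

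*Combined protocol and SAP*

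**What the plan says.** Section 5.3 makes APC (superiority) and PPA (non-inferiority) co-primary, and "both tests must successfully reject H0 in order to declare overall endpoint success". ADR is a secondary endpoint (Section 5.4), but Section 13 gives it a stated power of 90%, "based on the expected ADR of 35% in the control arm, and 45% for the intervention arm".

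The interim rule in Section 13 has four steps:

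1. At about 600 subjects, conditional power is calculated for APC, PPA and ADR. A value below 90% on any one of them leads to consideration of an increase to at most 2,400.
2. The increase is judged on the chance of succeeding on "both co-primary endpoints (APC and PPA) and success on the ADR endpoint".
3. The extra subjects are enrolled on this condition: "If the increase in sample size leads to an increase in the power for these endpoints to approximately 90" percent.
4. "Otherwise, the study may continue to the originally planned sample size of 1200 or stopped for futility".

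The final test combines the interim and post-interim Z statistics with weights of one half each.

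Two sentences send interim detail to the SAP. Section 12.5 says "A detailed unblinding and a communication plan will be provided in the statistical analysis plan", and Section 13 says "Communication processes will be laid out in the interim analysis section of the statistical analysis plan". Neither mentions a futility threshold, and the SAP's interim section is not part of the text reviewed. Separately, Section 12.8 lets the sponsor "terminate the study at any time for any reason at the sole discretion of the sponsor".

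**The concern.** Failing to reach 90% power is a reason not to enlarge a trial. It does not show that the trial will probably fail. Yet in the reviewed text it is the only way into the futility option, and nothing says how to choose between continuing and stopping.

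ADR is one of the endpoints that must reach the target. A trial likely to succeed on APC and PPA, which are all that overall success requires, could therefore arrive at the futility option because a secondary endpoint looked only moderately promising. ADR's stated power (90%) is also the lowest of the three: APC is given as above 99% and PPA as above 90%. ADR is thus a likely way in.

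The plan does not say which effect conditional power assumes, and the frequency of the problem depends heavily on that. At stake would be an avoidable stop, reported as futility, of a trial that would have met its objective.

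**Working it through.** **Inputs.** From Section 13: 600 per arm, 15% data loss, ADR 35% versus 45%, one-sided 0.025, interim at about 600 subjects (300 per arm), maximum 2,400, weights ½ and ½. Evaluable at 1,200: 600 × 0.85 = 510 per arm.

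**The plan's own figure.** The expected final Z for ADR is 0.10 / √[(0.45×0.55 + 0.35×0.65)/510] = 0.10 / √(0.475/510) = 3.277. Power is Φ(3.277 − 1.960) = 90.6%, which agrees with the stated 90%.

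**Conditional power (CP).** The test succeeds if √½·(Z1 + Z2) > 1.960, that is, if Z2 > 2.772 − Z1. Hence CP = Φ(E[Z2] + Z1 − 2.772). The second stage has 300 per arm for a total of 1,200 and 900 per arm for 2,400.

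*Interim trend.* E[Z2] is Z1 at 1,200 and √3·Z1 at 2,400.

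- CP at 2,400 is below 90% when Z1 < (2.772 + 1.282)/2.732 = 1.484.
- At that edge, CP at 1,200 is Φ(2×1.484 − 2.772) = Φ(0.196) = 58%.
- Under 35% versus 45%, Z1 has mean 3.277/√2 = 2.317, so the branch opens with probability Φ(1.484 − 2.317) = 20.2%.
- If all 300 per arm are evaluable at the interim, the mean is 0.10/√(0.475/300) = 2.513 and the probability is Φ(−1.029) = 15.2%.

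*Planned effect.* E[Z2] at 2,400 is √3 × 2.317 = 4.013.

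- CP is below 90% only when Z1 < 0.040 (unrounded), with probability Φ(0.040 − 2.317) = 1.1%.
- With 300 evaluable per arm it is Φ(−0.299 − 2.513) = 0.2%.

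Among the trials that enter the branch (510 evaluable per arm), ADR would still succeed at 1,200 in 67% (trend) and 24% (planned effect).

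**Co-primaries on track, ADR alone opening the branch.** This was simulated, requiring CP of at least 90% at 1,200 for APC and PPA, and CP below 90% at 2,400 for ADR. Assumptions not in the plan: APC power exactly 99%, PPA power 90–99%, PPA independent of the other two. An assumed negative binomial adenoma count, with 35–45% of patients having at least one adenoma and a mean of 0.55–1.0, puts the APC–ADR correlation at 0.64–0.85.

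| Evaluable per arm at interim | Interim trend | Planned effect |
|---|---|---|
| 255 (15% loss) | 5.0–9.5% | 0.3–0.7% |
| 300 | 3.0–6.5% | about 0.1% or less |

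If the trials in the first row continued to 1,200, both co-primaries would succeed in about 98% or more (trend) and about 92–96% (planned effect).

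**What the figures count.** Each is the chance of reaching a point where the plan allows either continuing to 1,200 or stopping. None is a probability of stopping.

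**The case for a change.** The best case for a change is that a discretionary stop with no criterion, recommended from unblinded data to a committee inside the sponsor, is where prespecification matters most. The general right to terminate in Section 12.8 does not justify a rule that can label a promising trial futile. The SAP is promised for unblinding and communication, not for a futility threshold. The gap between 1.1% and 20.2% comes entirely from an effect assumption the plan does not state.

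Much of this stands. The reading of the text and the arithmetic are right, and a threshold in the SAP's interim section can be neither confirmed nor ruled out.

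It does not establish harm, however. For harm to follow, people who see both co-primaries with at least 90% conditional power would have to choose to stop when continuing is expressly open to them. ADR's place in the decision also looks deliberate, since Section 13 gives power for ADR and names it among the objectives that conditional power assesses. Whether it should weigh in stopping is the sponsor's judgement.

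The obvious replacement is no clear gain. Take a rule that continues to 1,200 unless trend CP at 2,400 is below 20% for APC or PPA. Its cut is Z1 < (2.772 − 0.842)/2.732 = 0.706. It judges futility at a size those trials would not reach: CP at 1,200 there is Φ(2×0.706 − 2.772) = Φ(−1.360) = 8.7%. If always followed, it would stop 2.0–6.6% of trials in which the planning assumptions hold and cost 1.4–3.0 points of co-primary power.

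**Conclusion.** No change follows. The reviewed text gives no futility criterion and does not state the effect behind conditional power, and an ADR shortfall alone can open the option to stop. If ADR is truly 35% versus 45%, that happens in about 15–20% of trials under the interim trend and 0.2–1.1% under the planned effect. With both co-primaries on track, it happens in about 3–10% and under 1%, given a correlation of 0.64–0.85 and the assumed APC and PPA powers.

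The branch is permissive, so following the plan as written never forces a stop. A futility stop cannot inflate type I error, and the equal-weight combination test is untouched. The sponsor could end the study without this sentence. The remaining gap is one of detail: the effect assumed, whether 90% is joint or per endpoint, and how to choose between continuing and stopping. A competent interim statistician would settle these when preparing the interim programs, and the validity of the final APC and PPA conclusions does not depend on how they are settled.
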